3.2.3 Dosing Schedule

The dose level of PUL-042 Inhalation Solution in this study will be 20.3 µg Pam2 : 29.8 µg ODN/mL (50 µg PUL-042). A total of up to 3 doses will be administered over a 1-week period for a total dose of 60.9 µg Pam2 : 89.4 µg ODN.

Doses of PUL-042 or placebo will be prepared by an unblinded pharmacist and administered to the subject within 4 hours of preparation.

Doses will be administered via nebulization to deliver 4 mL using a PARI Sprint nebulizer equipped with a filter valve to prevent aerosol generation. The nebulizer will be operated until all drug is delivered.

3.2.4 Subject Compliance

Any material deviation from study procedures (identified by site personnel or monitor) will be documented. Major subject-level deviations will be captured on the protocol deviation form. A list of protocol deviations will be compiled and reviewed by the PI and Sponsor to identify major and minor deviations periodically using the criteria specified in the Protocol, Section 14.5.

4. GENERAL CONSIDERATIONS FOR DATA ANALYSIS

Unless otherwise specified, continuous variables will be summarized using descriptive statistics

(n, mean, standard deviation, median, minimum, and maximum). Categorical variables will be summarized showing the number and percentage of subjects within each category.

Summary results will be provided for each treatment group. All tabulations will be based on pooled data across centers.

Unscheduled visits will be excluded from the summaries but will be included in the data listings.

All statistical tests will be two-sided and tested at the 5% level of significance.

Analyses will be performed using SAS for Windows statistical software, version 9.4 or higher (SAS, Cary, NC), except where other software may be deemed more appropriate.

CTI will perform all efficacy and safety analyses described in this SAP.

Subject data will be listed, sorted by treatment group and subject number. When applicable, listings will be additionally sorted by visit and assessment date/time.

4.1 Data Quality Assurance

Once all the source verification is complete, all queries are resolved, and the database has been updated appropriately, the database will be locked and made available to CTI Biostatistics for final analysis.

Data may be pulled by CTI Biostatistics for DSMB analysis at a time when source verification and query resolution is ongoing.

All SAS programs used to create analysis data sets, tables, and listings are double programmed. The SAS outputs will be compared and the programs will be updated until the outputs match.

4.2 Analysis Sets

The following two analysis sets will be defined for this study:

Intent to Treat (ITT) Set

The ITT set is defined as all randomized subjects who receive at least one dose of experimental treatment (i.e., PUL-042 or Placebo). The primary analysis of all efficacy endpoints will be carried out using the ITT set based on the randomized treatment.

Safety (SAF) Set

The SAF set is also defined as all randomized subjects who receive at least one dose of experimental treatment (i.e., PUL-042 or Placebo), but subjects are categorized based on the treatment actually received rather than as randomized. All safety and tolerability analyses will be carried out using the SAF set. If, as expected, the Safety analysis set is redundant (i.e., is identical to the ITT analysis set), the ITT set will be used for the assessments of safety and tolerability.

4.3 Assessment Windows

Data will be summarized by nominal study visit recorded in the database.

4.4 Handling of Dropouts or Missing Data

Except for the time to event endpoints (Table 1), partial end dates of prior and concomitant medications (Section 5.6), and partial onset dates of AEs (Section 7.2.1), all other missing data

will be treated as missing and no method for imputation is planned.

Missing data on the time to event endpoints will have events coded as right censored per the following table:

Table 1 Missing Data Coding for Time to Event Data Analyses

Endpoint	Right Censoring
Time to clinical improvement on Ordinal Scale	Subject who did not meet the criteria for clinical improvement on Ordinal Scale or died at any time during follow-up will be right censored as of the date of last non-missing assessment of Ordinal Scale on or prior to Day 29.
Time to resolution of disease	Subject who did not meet the criteria for the resolution of disease or died at any time during follow-up will be right censored as of the date of last non-missing assessment of Ordinal Scale on or prior to Day 29.
Time to resolution of symptoms	Subject who did not meet the criteria for the resolution of symptoms or died at any time during follow-up will be right censored as of the date of last non-missing assessment of symptoms on or prior to Day 29.
Time to clinical improvement on symptoms	Subject who did not meet the criteria for clinical improvement on symptoms or died at any time during follow-up will be right censored as of the date of last non-missing assessment of symptoms on or prior to Day 29.
Subject Survival	Subjects who are still alive as of the last known follow-up will be right censored as of the date of last subject contact when the subject was known to be alive.

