6.1 Primary Efficacy Endpoint and Analysis

The primary efficacy variable is the clinically meaningful worsening of COVID-19 within 28 days from the start of experimental therapy.

The Ordinal Scale for Clinical Improvement is a 9-point scale that measures disease severity. For this study, an increase of 2 or more points is considered meaningful worsening of disease ([Table 2](#)). This endpoint considers changes in disease severity that are observed at any time over the course of this study.

The Ordinal Scale for Clinical Improvement to be used in this study is derived from a draft scale proposed by the World Health Organization^[1] for clinical improvement as presented below:

Table 2 Ordinal Scale for Clinical Improvement (Derived from draft WHO scale)^[1]

Descriptor	Score
No clinical or virological evidence of infection	0
Infected but no limitation of activities	1
Limitation of activities	2
Hospitalized not requiring oxygen therapy (SpO ₂ > 93% on room air)	3
Oxygen by mask or nasal prongs	4
Non-invasive ventilation or high-flow oxygen	5
Intubation and mechanical ventilation	6
Ventilation + additional organ support- pressors, RRT, ECMO	7
Death	8

The null hypothesis is that there is no difference in proportions of subjects with clinically meaningful worsening of COVID-19 through Day 29 between randomized treatment groups; $H_0: \pi_t - \pi_c = 0$. The alternative hypothesis is that the proportions of subjects with clinically meaningful worsening of COVID-19 through Day 29 are different between the treatment groups; $H_1: \pi_t - \pi_c \neq 0$.

Subjects who had an increase of 2 or more points in Ordinal Scale from the baseline will be treated as meeting the criteria for clinically meaningful worsening of COVID-19. The proportion of subjects who met the criteria within each treatment group will be presented along with a two-sided exact (Clopper-Pearson) 95% confidence interval (CI).

The observed difference in the proportion of subjects meeting the criteria between treatment groups along with the exact unconditional 95% CI for risk difference will be calculated. The null hypothesis will be tested using Fisher's exact method and the p-value will be reported.

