6.2 Secondary Efficacy Endpoints and Analyses

Clinically meaningful worsening of COVID-19 through Day 15

The analysis of the proportion of subjects who met the criteria of an increase of at least 2 points on the Ordinal Scale for Clinical Improvement through Day 15 within each treatment group will be performed using the method described above in Section 6.1.

Ordinal Scale for Clinical Improvement

Clinical improvement is defined as a reduction of at least 1 point on the Ordinal Scale. The time to the first occurrence of clinical improvement will be estimated using the KM method. The KM estimates along with 95% CI, and survival curves will be provided. Based on the KM estimates, the probabilities of experiencing clinical improvement and associated 95% CIs on Days 15 and 29 will be reported; in addition, the 25%, 50% (median), and 75% percentiles of the time to clinical improvement with associated 95% CIs will be provided, as data permit. The survival rates between treatment groups will be compared using Log-rank test. The p-value from Log-rank test will be presented.

In addition, the time to the first occurrence of resolution of COVID-19 defined as an Ordinal Scale of 0 will also be evaluated, using the KM method described above for the analysis of time to clinical improvement.

The progression of COVID-19 severity as measured by the Ordinal Scales through Day 29 will be evaluated by graphical illustrations using stacked bar chart for each treatment group. The X axis representing time points and Y axis representing the cumulative number of subjects for each Ordinal Scale. Each bar is divided into a number of sub-bars stacked end to end corresponding to different Ordinal Scales.

The changes in Ordinal Scales through Day 29 will be examined using box and whisker plots for each treatment group. The X axis representing the post-baseline time points and the Y axis representing the change from baseline in Ordinal Scales at each post-baseline visit.

The absolute value and change from baseline in the Ordinal scale from Day 1 through Day 29 will be summarized by treatment group and visit using descriptive statistics.

Symptom Score

The symptoms due to SARS-CoV-2 infection will be assessed and the symptom scores (Cough (0-3), Shortness of breath or difficulty breathing (0-3), Muscle aches or fatigue (0-3), Fever (0-4)) will be recorded in the eCRF.

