The respiratory symptom score will be calculated by summing the symptom scores from Cough and Shortness of breath or difficulty breathing. The scores from each symptom together with calculated respiratory symptom scores will be summarized by presenting the number and percentage of subjects for each category by visit and treatment group.

The time to the first occurrence of resolution of symptoms defined as the time from the first symptom score of ≥ 1 to a symptom score of 0 will be estimated using the KM method. If a subject had a symptom score of 0 from Baseline through Day 29, then that subject will be excluded from the analysis.

Time to Resolution of Symptoms (days) = (Date of the first symptom score of 0 since the initial score of ≥ 1) - (Date of the initial symptom score of ≥ 1 at or after Baseline) + 1

For each individual symptom and the respiratory symptoms (cough, shortness of breath and difficulty breathing), the KM estimates along with 95% CI, and survival curves will be provided. Based on the KM estimates, the probabilities of experiencing the resolution and associated 95% CIs on Days 15 and 29 will be reported; in addition, the 25%, 50% (median), and 75% percentiles of the time to resolution with associated 95% CIs will be provided, as data permit. The survival rates between treatment groups will be compared using Log-rank test. The p-value from Log-rank test will be presented.

In addition, the time to the first occurrence of improvement of symptoms defined as the time from the initial symptom score of ≥ 1 to a reduction of ≥ 1 point on initial symptom score will also be evaluated for each individual symptom and the respiratory symptoms (cough, shortness of breath and difficulty breathing), using the KM method described above for the analysis of time to resolution of symptoms.

If a subject had a symptom score of 0 from Baseline through Day 29, then that subject will be excluded from the analysis.

Time to Improvement of Symptoms (days) = (Date of the first reduction of ≥ 1 point on initial symptom score of ≥ 1) - (Date of the initial symptom score of ≥ 1 at or after Baseline) + 1

A radar plot will be created by presenting each symptom score at each time point by treatment group.

SARS-CoV-2 Test

The SARS-CoV-2 tests will be performed at the end of the study or early discontinuation visit.

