Subjects who have died without ICU admission during the study will be counted as requiring ICU admission for the analysis.

Number of ICU Days

The number of ICU days from Day 1 to Day 29 will be calculated based on the ICU admission and discharge dates recorded in the eCRF. The calculated number of ICU days will be compared between treatment groups using 2-sided Student's t-test. The 95% CI and p-value will be presented.

If the Student's t-test normality assumption is found to be clearly violated, a sensitivity analysis will be performed using a non-parametric Wilcoxon rank-sum test. The p-value from the test will be presented.

Subjects who died will be assigned as hospitalized in the ICU for the number of days remaining from the day of death to Day 29 for the analysis. Subjects who are alive and never admitted into the ICU will be included in the analysis with a value of zero ICU days.

Subjects who were at ICU at study completion will be assigned an ICU end date equal to the date of completion for the purpose of deriving number of ICU days.

Subjects requiring mechanical ventilation

Subject data pertaining to mechanical ventilation use will be recorded in the database.

The proportion of subjects who were on mechanical ventilation from Day 1 to Day 29 within each treatment group will be analyzed and compared using the method described above for the analysis of subjects requiring ICU admission.

Subjects who have died without mechanical ventilation during the study will be counted as requiring mechanical ventilation for the analysis.

Number of days on mechanical ventilation

The number of days on mechanical ventilation from Day 1 through Day 29 will be calculated based on the start/stop dates of mechanical ventilation recorded in the eCRF. Number of days on mechanical ventilation will be compared between treatment groups using 2-sided Student's t-test. The 95% CI and p-value will be presented.

If the Student's t-test normality assumption is found to be clearly violated, a sensitivity analysis will be performed using a non-parametric Wilcoxon rank-sum test. The p-value from the test will be presented.

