Subjects who died will be assigned as being on mechanical ventilation for the number of days remaining to Day 29 for the analysis. Subjects who had mechanical ventilation ongoing at study completion will be assigned a mechanical ventilation end date equal to the date of completion for the purpose of deriving duration of mechanical ventilation. Subjects who are alive and never placed on mechanical ventilation will be included in the analysis with a value of zero days on mechanical ventilation.

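### Deaths without improvement are censored at the last assessment, so the Kaplan-Meier probabilities of improvement or resolution at Days 15 and 29 are too high, most of all in an arm with more such deaths

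*SAP*

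**What the plan says.** Table 1 in SAP 4.4 sets the censoring for five time-to-event endpoints. Four concern improvement or resolution. For the two on the Ordinal Scale, a subject who "died at any time during follow-up will be right censored as of the date of last non-missing assessment of Ordinal Scale" leaves the risk set at that assessment. For the two on symptoms, the rule is that a subject who "died at any time during follow-up will be right censored as of the date of last non-missing assessment of symptoms" does the same. Apart from stated exceptions for partial dates and for Table 1 itself, missing data "will be treated as missing and no method for imputation is planned".

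SAP 6.2 analyses these endpoints by Kaplan-Meier and log-rank. For the Ordinal Scale it says that "the probabilities of experiencing clinical improvement and associated 95% CIs on Days 15 and 29 will be reported"; for symptoms, that "the probabilities of experiencing the resolution and associated 95% CIs on Days 15 and 29 will be reported". No competing-risk estimator appears anywhere in the SAP.

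Elsewhere death is treated as the worst outcome. SAP 6.1 states that "The Ordinal Scale for Clinical Improvement is a 9-point scale that measures disease severity", and its Table 2 gives death the top score of 8. For ICU days, "Subjects who died will be assigned as hospitalized in the ICU for the number of days remaining" up to Day 29. For ventilator days, "Subjects who died will be assigned as being on mechanical ventilation for the number of days remaining to Day 29 for the analysis".

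**The concern.** Kaplan-Meier assumes that a censored subject has the same future chance of the event as those still under observation. That is reasonable for someone who moves away. It is false for someone who has died without improving, whose chance is zero. Censoring at the last visit passes that subject's weight to the survivors, so one minus Kaplan-Meier (1-KM) can never fall below the true proportion improved. It exceeds that proportion whenever anyone in the arm improves after the censoring.

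The error grows with the number of deaths without improvement, so in a comparison it favours the arm with more of them. A reader who takes the Day 15 and Day 29 figures as the chance of recovery would be misled in the direction that matters most for a drug under safety surveillance for mortality.

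A second difficulty lies in the same sentence. Read literally, it also censors a subject who improved and later died. That discards a real event and lowers 1-KM. Two programmers could code the row differently.

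**Working it through.** The plan gives no expected improvement probability, so there is no stated figure to reproduce.

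**Inputs from the documents.** 50 per arm (SAP 9); post-baseline Ordinal Scale visits on Days 3, 6, 10, 15 and 29 (SAP Appendix A); mortality of 5% and 15%, which appear only as illustrations for the stopping rule (SAP 8).

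**Assumed.** In an arm of 50, improvements at the five visits number 4, 6, 6, 7 and 7. That makes 23 by Day 15 (true 23/50 = 46.0%) and 30 by Day 29 (true 30/50 = 60.0%). Deaths fall among the 20 who never improve.

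**Basic case, last score on Day 6.** After Day 6, S = (46/50)(40/46) = 0.80 with 40 at risk. If d deaths are censored there, 40 − d are at risk at Day 10. The later factors telescope:

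- Day 29: 1-KM = 1 − 0.80 × (20 − d)/(40 − d)
- Day 15: 1-KM = 1 − 0.80 × (27 − d)/(40 − d)

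| Deaths d | Day 15 (true 46.0%) | Day 29 (true 60.0%) |
|---|---|---|
| 0 | 46.0% | 60.0% |
| 2 | 47.4% | 62.1% |
| 3 | 48.1% | 63.2% |
| 5 | 49.7% | 65.7% |

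**Timing of the last score, 2 to 3 deaths (5% of 50 = 2.5).** Lowest: 2 deaths last scored on Day 15, 1 − 0.54 × 18/25 = 61.1%. Highest: 3 deaths last scored on Day 1, 1 − 17/47 = 63.8%. The excess is 1.1 to 3.8 points. The standard error of one arm's proportion is √(0.6 × 0.4/50) = 6.9 points.

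**A higher improvement rate.** With 40 improvers (5, 8, 10, 8, 9 by visit; true 62.0% at Day 15, 80.0% at Day 29) and 3 deaths last scored on Days 6, 10 and 15, 1-KM is 63.7% and 84.1%. At Day 29 this is 1 − (37/50)(26/36)(17/25)(7/16).

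**Unequal mortality.** Let each survivor improve with probability 30/47.5 = 63.2% in both arms. True Day 29 proportions are 0.95 × 63.2% = 60.0% and 0.85 × 63.2% = 53.7%, a deficit of 6.3 points. Simulated mean 1-KM:

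- last score equally likely on Days 1, 3, 6, 10 and 15: 62.5% and 61.0%, an apparent deficit of 1.5 points;
- death dates uniform over follow-up, so about half the deaths have Day 15 as last score: 62.0% and 59.5%, an apparent deficit of 2.5 points.

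**Does score 8 rescue the Ordinal Scale rows?** The SAP does not say whether or when an 8 is entered as an assessment. A single 8 on the date of death only moves the censoring date. With 2 deaths on Day 8, 1-KM is 62.1%; on Day 20, 61.1%. Only an 8 carried to Day 29 restores 60.0%, and no carry-forward rule exists. The symptom scores have no value for death.

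**Literal wording.** Take 2 deaths, of whom k improved on Day 6 and are recoded as censored at Day 10, the others being censored unimproved at Day 6:

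- k = 0: 62.1%
- k = 1: 1 − 0.82 × (34/40) × (19/33) = 59.9%
- k = 2: 1 − 0.84 × (36/42) × (20/34) = 57.6%

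**Check of the fix.** Holding unimproved deaths in the risk set to the end, and counting prior improvement, gives 60.0% in every example with 30 improvers. With 5% mortality and 10% of survivors also lost to follow-up (simulated, true value about 60%), holding in the risk set gives 59.8%, cumulative incidence 59.9%, and the Table 1 rule 62.5%.

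**The case against.** The strongest reply is that little turns on this. Entry is limited to scores of 4 or less with preserved spirometry, and the SAP itself allows for no more than one death by the mortality look. At 5% mortality the excess is about 2 points against a standard error of 6.9. These are secondary endpoints in a study that SAP 4.5 calls exploratory. The arms are compared on them only by log-rank, which remains valid with deaths censored as a comparison of cause-specific rates. Death counts as worsening in the primary endpoint through score 8, and the mortality analysis and the stacked bar charts show deaths openly. All of that stands, and it limits the importance of the point. None of it corrects the reported probabilities.

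It can also be said that the direction is not settled, because the literal wording pulls the other way for subjects who improved and later died. That is true of the sentence as a whole. It does not alter the upward bias from deaths without improvement; it adds a second fault in the same sentence.

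Finally, recovery among those still alive is a legitimate target, and the treatment of death in the day-count endpoints does not formally bind Table 1. But 1-KM is not labelled as conditional. It is presented as the probability of experiencing the event, which it does not estimate when deaths occur.

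**Conclusion.** The concern holds. As written, the rule inflates the Day 15 and Day 29 probabilities for all four endpoints whenever subjects die without the event and others have it later. With 2 to 3 deaths in an arm of 50 and a true 60%, the Day 29 excess is 1.1 to 3.8 points. With 5% against 15% mortality, a 6.3-point deficit shrinks to about 1.5 to 2.5 points.

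These sizes rest on assumed improvement rates and death timing; 15% is a harm scenario and not an expected rate. The direction follows from the estimator alone. There is no bias without deaths, and it largely cancels between arms when deaths are equal. For the two Ordinal Scale endpoints the size also depends on how score 8 is recorded. The primary endpoint is unaffected and the log-rank test is not invalidated. The plan should be corrected, but its main conclusion does not depend on it.

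**What to change.** 1. In the four improvement and resolution rows of Table 1, state that a subject who dies without meeting the criterion stays in the risk set as event-free and is censored after the last possible event time on that endpoint's scale. The symptom clock starts at the first score of at least 1, so that time must be set on its own scale. Alternatively, report cumulative incidence with death as a competing event. Either rule should apply whether or not a score of 8 is entered.
2. State that improvement or resolution before death counts as an event on its own date.
3. If the log-rank test is kept with deaths censored, label it a cause-specific comparison.

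The cost is SAP wording and minor programming before unblinding. No new data are needed.

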7.11. Study Days 3, and 6 (Study Drug Administration)

All assessments should occur ± 1 day from the scheduled Study Day.

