7.11.3. Days 3 and 6 (T₀ +30 minutes [\pm 15 minutes])

- Vital signs
- Spirometry
- Adverse event assessment
- Concomitant medication assessment

7.12. Study Day 10

Assessments should occur \pm 1 day of target Study Day.

The following assessments will be conducted:

- Physical examination
- Vital signs
- SARS- CoV-2 infection symptom score
- Ordinal Scale for Clinical Improvement assessment
- Adverse event assessment
- Concomitant medication assessment

7.13. Study Day 15

Assessments should occur within +1 day of target Study Day.

The following assessments will be conducted:

- Physical examination
- Vital signs
- SARS- CoV-2 infection symptom score
- Ordinal Scale for Clinical Improvement assessment
- Adverse event assessment
- Concomitant medication assessment

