7.15. Study End (Day 29)

Assessments should occur within +2 days of target Study Day.

Subjects should be followed to Day 29 (28 days post-initial dose of study drug).

- Women who can become pregnant will take a urine pregnancy test. If the test is positive, the results will be confirmed with a blood pregnancy test.
- Nasopharyngeal or oropharyngeal sample for SARS-CoV-2 testing
- SARS- CoV-2 infection symptom score
- Ordinal Scale for Clinical Improvement assessment
- Adverse event assessment
- Concomitant medication assessment

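### Read literally, SAP Table 1 caps censoring but not events at Day 29, although the Study End visit may fall on Days 29 to 31, so late-seen non-responders are censored back to about Day 15

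*SAP*

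**What the plan says.** **Visit windows.** Protocol 7.13 (Day 15): "Assessments should occur within +1 day of target Study Day". Protocol 7.15 (Study End, Day 29): "Assessments should occur within +2 days of target Study Day". Both windows run late only. Days 3, 6 and 10 have two-sided windows of one day (Protocol 7.11 and 7.12).

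**Censoring.** In SAP 4.4 Table 1, subjects without the event on the two Ordinal Scale endpoints are "right censored as of the date of last non-missing assessment of Ordinal Scale on or prior to Day 29", and those without the event on the two symptom endpoints are "right censored as of the date of last non-missing assessment of symptoms on or prior to Day 29". The table sets no corresponding limit on events. Survival is handled differently: subjects still alive are "right censored as of the date of last subject contact when the subject was known to be alive", with no Day 29 limit.

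**Time scale.** SAP 4.6 derives Study Day and duration from calendar dates, with first dosing as Day 1. SAP 6.2 gives date-difference formulas (plus 1) for the two symptom endpoints and no time formula for the two Ordinal Scale endpoints. SAP 4.3 says that data are summarised by the nominal visit in the database.

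**Read-outs.** For improvement on the Ordinal Scale, SAP 6.2 states that "the probabilities of experiencing clinical improvement and associated 95% CIs on Days 15 and 29 will be reported". The same is planned for resolution and for the symptom endpoints, each with a log-rank test.

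**The concern.** A visit that complies fully with the protocol can fall after the day at which the curve is read and after the day at which censoring stops. This has two consequences on the literal text.

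1. **Read-out.** An event first recorded on Day 16, or on Days 30 to 31, carries that day as its time and is absent from the Day 15 or Day 29 probability.
2. **Outcome-dependent censoring.** Take two subjects who both attend on Day 30. The one without the event is censored at the last assessment on or before Day 29, normally the Day 15 visit, so about two weeks of completed follow-up is dropped. The one with the event remains at risk until Day 30. Membership of the late risk set is then decided by the outcome, which Kaplan-Meier and log-rank methods do not allow.

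At stake are the reported Day 15 and Day 29 probabilities, the upper percentiles and the between-arm tests for improvement and resolution on the Ordinal Scale and on symptoms. Protocol section 5 says that the study's data will inform whether to advance to Phase 3.

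**Working it through.** The documents give no figure for this point, so there is nothing to reproduce. The windows and rules come from the sections cited above. The response rates and the share *q* of last visits made on Days 30 to 31 are assumptions.

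**One arm.** Take 100 subjects: 60 improved by the Day 15 visit, 20 more first seen improved at the last visit, 20 never improved. The proportion improved by the last visit is 80%. Lateness is unrelated to outcome.

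Under Table 1 read literally, 20*q* non-responders are censored at about Day 15. At Day 29 there are 40 − 20*q* at risk and 20(1 − *q*) events, so

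S(29) = 0.40 × [1 − 20(1 − *q*)/(40 − 20*q*)] = 8/(40 − 20*q*).

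| q | S(29) | KM at Day 29 | KM at Day 31 |
|---|---|---|---|
| 0 | 8/40 = 0.200 | 80.0% | 80.0% |
| 10% | 8/38 = 0.211 | 78.9% | 100% |
| 25% | 8/35 = 0.229 | 77.1% | 100% |
| 50% | 8/30 = 0.267 | 73.3% | 100% |
| 75% | 8/25 = 0.320 | 68.0% | 100% |

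The 100% arises because, after Day 29, the number still at risk is (40 − 20*q*) − 20(1 − *q*) events − 20(1 − *q*) non-responders censored on Day 29 = 20*q*. All of these are responders, so the curve runs to its end for any *q* above zero.

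The two effects pull in opposite directions at Day 29. With *q* = 50% and non-responders censored on their actual visit dates, KM at Day 29 is 1 − 0.40 × (1 − 10/40) = 70.0%. Back-censoring lifts this to 73.3%; the shortfall from 80% comes from the read-out day.

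**Day 15.** If 40% have improved by Day 10 and 25% are first seen improved at the Day 15 visit, half of whom attend on Day 16, the Day 15 estimate is 40 + 12.5 = 52.5% against 65% by visit.

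**Two arms, equal lateness.** Take 100 per arm, 60% improved by Day 15 in both, then 90% against 70% by the last visit, with *q* = 50% in each arm. All events up to Day 15 are placed at one time and all late visits on Day 31.

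- *Nominal visit.* Day 29: 40 at risk per arm, 30 and 10 events. O − E = 30 − 20 = 10. Variance = 12.06 (Day 15) + 5.06 (Day 29) = 17.12. Chi-square = 100/17.12 = 5.84 (p = 0.016). KM is 90% against 70%.
- *Table 1 read literally.* Day 29: 35 and 25 at risk, 15 and 5 events. E = 20 × 35/60 = 11.67, so O − E = 3.33. Variance = 12.06 + 3.30 = 15.36. On Day 31 everyone at risk has the event, which adds nothing. Chi-square = 11.11/15.36 = 0.72 (p = 0.39). KM at Day 29 is 1 − 0.40 × 20/35 = 77.1% against 1 − 0.40 × 20/25 = 68.0%, a difference of 9.1 points in place of 20.
- *Actual dates, non-responders censored at their real last visit.* O − E = 5 + 5 = 10. Variance = 12.06 + 3.80 + 2.56 = 18.42. Chi-square = 5.43.

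At the trial's 50 per arm (88% against 68% after rounding to whole subjects) the first two chi-squares are 2.91 and 0.39. The loss in the test comes from the one-sided cap; calendar timing alone costs little there.

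**The case against.** **Day 29 may mean the visit.** Day 29 is also the label of Visit 7 in the schedule of events, and SAP 4.3, under a heading on assessment windows, points to nominal visits. If Table 1 means the visit, nobody is censored back and the outcome dependence disappears. This stands as a possible reading. A reader might infer that the SAP fixes calendar timing for all these endpoints; it does not, since the Ordinal Scale endpoints have no time formula. But SAP 4.3 speaks only of summaries and Table 1 speaks of dates, so the question is open. Even on the visit reading, the symptom formulas put a Day 16 event, counted from Day 1, beyond the Day 15 read-out.

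**Not every endpoint or visit is affected.** A reader might also infer that all four endpoints are uniformly biased downward. That goes too far. Visits held on Day 15 or Day 29 itself are counted. A symptom first scored on Day 3 and resolved on Day 31 has time 31 − 3 + 1 = 29 and is counted. If Ordinal Scale time were elapsed days without the added 1, Day 16 would be time 15 and Day 30 would be time 29; only Day 31 would miss its read-out.

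**Late events stay in the log-rank test, and blinding should balance lateness.** Both points are fair. Neither removes the problem on the literal reading: the two-arm example has equal lateness, and its late events carry no treatment information because only responders remain at risk.

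**The endpoints are secondary and the size is assumed.** This stands. SAP 4.5 calls the study exploratory, and the documents do not give the share of late visits.

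**Conclusion.** The concern holds in a limited form. On its literal wording, SAP Table 1 makes censoring depend on outcome for subjects whose Study End visit falls on Days 30 to 31, and date-based timing from Day 1 moves events seen on Day 16 or Days 30 to 31 past the planned read-outs. The nominal-visit reading would avoid the back-censoring, but the SAP does not adopt it for these endpoints.

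Under the assumed 80% response, the Day 29 estimate falls by 1.1 points with 10% of last visits late, 2.9 points with 25% and 6.7 points with 50%; with none late there is no effect. The two-arm loss is likewise an illustration resting on assumed response rates and half the last visits being late.

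The finding covers the secondary Ordinal Scale and symptom time-to-event endpoints only. The primary endpoint is a proportion tested by Fisher's exact method, and survival has no Day 29 cap on censoring. It should be corrected before unblinding.

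**What to change.** In SAP 4.4 and 6.2:

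- Assign the nominal visit day (1, 3, 6, 10, 15, 29) as the time for both events and censoring at scheduled visits.
- Apply one cut-off to both: the Day 29 visit, including its window.
- Give a time formula, with its origin, for the two Ordinal Scale endpoints.

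With nominal days the one-arm example returns 80% at Day 29 for every share of late visits.

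Keeping actual dates and reading the curve at Days 16 and 31 is not a substitute. With *q* = 50% and all late visits on Day 31, it gives 1 − 0.40 × (1 − 10/40) × (1 − 10/20) = 85% against 80%.

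The cost is a few sentences in the SAP and one programming rule. No change to visits or data collection is needed.
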